5.2.1. Analyses for Binary Data

Descriptive statistics for binary variables are the proportion (%) and the numerator (n) and the denominator (N) used in the proportion calculation. The 95% CI for percentage, and for the difference in percentages, will also be presented, where applicable.

1. The 95% CI for the proportion (within–vaccine group) will be constructed by the Clopper-Pearson method described by Newcombe.³ The 95% CI will be presented in terms of percentage.
2. The 95% CI for the difference in the proportions (between–vaccine group) will be computed using the Miettinen and Nurminen method.⁴ The 95% CI will be presented in terms of percentage.

5.2.2. Analyses for Continuous Data

Unless otherwise specified, descriptive statistics for continuous variables are n, mean, median, standard deviation, minimum, and maximum.

The CI for the mean of the continuous variable will be constructed by the standard method based on Student’s t-distribution.

5.2.2.1. Geometric Means

Continuous immunogenicity endpoints will be logarithmically transformed for analysis. Geometric means and the associated 2-sided 95% CIs will be derived by calculating group means and CIs on the natural log scale based on the t-distribution and then exponentiating the results.

5.2.2.2. Geometric Mean Fold Rises

GMFRs will be calculated as the group mean of the difference of logarithmically transformed assay results (later time point minus earlier time point) and exponentiating the mean. GMFRs are limited to participants with nonmissing values at both time points. The associated 2-sided 95% CIs will be obtained by constructing CIs using Student's t-distribution for the mean difference on the logarithm scale and exponentiating the confidence limits.

5.2.2.3. Geometric Mean Ratios

The GMRs will be calculated as the mean of the difference of logarithmically transformed assay results between 2 groups (coadministration group to sequential-administration group) and exponentiating the mean. Two-sided CIs will be obtained by calculating CIs using Student's t-distribution for the mean difference of the logarithmically transformed assay results and exponentiating the confidence limits.

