8.1.2.2. RSV Vaccine Antibody Testing

Serum samples collected at all 3 visits will be assayed for RSV A and RSV B serum NTs CCI
[REDACTED]

RSV A and RSV B serum NTs will be determined and reported as the NT. CCI
[REDACTED]

Sample collection, processing, storage, and shipping information can be found in the laboratory manual. All assays will be performed by Pfizer and/or at a facility designated by Pfizer.

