8.1.2.3. SIIV Immune Response Testing

HAI titers to the influenza strains in the SIIV administered will be determined on sera collected at Visits 1 and 2 (prior to and 1 month after SIIV administration).

H3N2-neutralizing antibody titers may be determined if the H3N2 strain in the SIIV fails to hemagglutinate or hemagglutinates via neuraminidase rather than hemagglutinin, which may invalidate the HAI assay for H3N2.

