9.1.2. Statistical Hypotheses

9.1.2.1. Statistical Hypothesis for Primary RSV Immunogenicity

The primary immunogenicity objective on immune response elicited by RSVpreF will be evaluated by the following hypothesis for both RSV A and RSV B as measured by NT:

$$H_{01}: \ln(\mu_1) - \ln(\mu_2) \leq \ln(0.667)$$

where $\ln(0.667)$ corresponds to a 1.5-fold margin for noninferiority and $\ln(\mu_1)$ and $\ln(\mu_2)$ are the natural log of the geometric mean of NT at 1 month after vaccination with RSVpreF for the coadministration group (Visit 2) and the sequential-administration group (Visit 3), respectively. Noninferiority will be declared if the lower limit of the 2-sided 95% CI for the GMR (coadministration group to sequential-administration group) is >0.667 for both RSV A and RSV B NTs.

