9.1.3. Multiplicity Adjustment

No multiplicity adjustment will be applied for this study. The primary objectives of noninferiority will be achieved only if the 1.5-fold equivalence criterion is met for each strain included in SIV and for both RSV A and RSV B antigens simultaneously. Each of the 6 statistical tests (4 from the SIV objective and 2 from the RSV objective) will use a 2-sided alpha level of 0.05.

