9.5. Sample Size Determination

Table 9 presents the power to demonstrate that the immune responses induced by coadministration of RSVpreF and SIIV are noninferior to the administration of RSVpreF or SIIV alone.

For both NT and HAI assay results, it is assumed that true ratios of the coadministration group to the sequential-administration group are not larger than 0.9 (or -0.105 with the natural log scale). The SDs of the log titers are based on Study C3671001 data.

Considering this is a short study among older adults, it is reasonable to assume a 7-8% nonevaluable rate; consequently, enrolling approximately 1400 participants in the study will provide a sample size of approximately 1300 participants to be included in the evaluable population analysis. With 650 evaluable participants per vaccine group and the above assumptions, the power is 81.6% to declare noninferiority for all 4 strains included in SIV and both RSV A and RSV B. Power was calculated with PROC POWER in SAS using the TWOSAMPLEMEANS statement.

Table 9. Sample Size Determination

Antigen	Common SD (Log e Scale) ^a	Difference (Log e Scale)	Noninferiority Margin	Power to Declare Noninferiority (1-Sided Alpha = 0.025)
RSV A	1.3	0.105	1.5-fold	98.6%
RSV B	1.4	0.105	1.5-fold	97.1%
H1N1	1.3	0.105	1.5-fold	98.6%
H3N2	1.7	0.105	1.5-fold	88.9%
B Strain 1	1.3	0.105	1.5-fold	98.6%
B Strain 2	1.3	0.105	1.5-fold	98.6%
Overall power to reject all 6 tests				81.6%

a. The reference study is C3671001. The maximum SD across all age/vaccine groups was used for each antigen/strain.

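### All six primary GMRs use an unadjusted t-interval although a pre-vaccination titer is assayed for every endpoint, so precision is given up in a trial already cut to 1400 participants

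*SAP*

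**What the plan says.** SAP 5.2.2.3 and Protocol 9.3.1.2.3 give the estimator in the same words: "The GMRs will be calculated as the mean of the difference of logarithmically transformed assay results between 2 groups". The group difference on the log scale is exponentiated and given a Student t confidence interval. SAP 6.1.1.1 (RSV A and B) and 6.1.2.1 (each influenza strain) both refer to that section. The supplementary mITT analyses (SAP 6.1.1.2 and 6.1.2.2) reuse the method, and SAP 6.4 adds only a split by age group. No model with a baseline covariate appears for any primary endpoint.

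The baseline values are nevertheless planned. Protocol 8.1.2.1 has blood drawn before vaccination at Visit 1. For RSV, Protocol 8.1.2.2 states: "Serum samples collected at all 3 visits will be assayed for RSV A and RSV B serum NTs". For influenza, Protocol 8.1.2.3 states: "HAI titers to the influenza strains in the SIIV administered will be determined on sera collected at Visits 1 and 2". SAP 3.1.4.2 plans the same two visits for the fallback H3N2 neutralization assay. These Visit 1 titers are used only for secondary GMTs and fold rises and for exploratory seroprotection and seroconversion.

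On power, Protocol 9.5 states: "With 650 evaluable participants per vaccine group and the above assumptions, the power is 81.6% to declare noninferiority" on all four strains and both RSV subgroups. Amendment 1 reduced enrollment from 2230 to 1400 because of operational delays.

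**The concern.** Protocol 2.3.1 describes older adults as universally RSV-experienced, and the seroconversion rule in SAP 3.2.1.3 provides for participants who already have measurable HAI titers. Participants therefore enter with pre-existing antibody, and the pre-vaccination titer is the natural predictor of the titer one month after vaccination. An unadjusted interval keeps that between-person variance in the error term. Any chance difference in baseline titers between the groups also stays in the point estimate.

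The power margin is thin. All six comparisons must succeed together, so the weakest one, H3N2, dominates. The sample was reduced by more than a third, and the power calculation was redone with unadjusted SDs. The assumed true ratio of 0.9 may also be optimistic. Protocol 2.2.1 reports that influenza responses trended lower with coadministration in one Phase 1/2 study, and were similar or slightly lower in the other. Baseline adjustment is the obvious way to recover precision without more participants.

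**Working it through.** **Inputs**

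- Alpha: each test "will use a 2-sided alpha level of 0.05" (Protocol 9.1.3), that is 0.025 one-sided for noninferiority. All six tests must pass.
- Margin: 0.667, which "corresponds to a 1.5-fold margin for noninferiority" (Protocol 9.1.2.1). −ln(0.667) = 0.405.
- True ratio: "it is assumed that true ratios of the coadministration group to the sequential-administration group are not larger than 0.9" (Protocol 9.5), a log difference of 0.105.
- SDs of log titer (Protocol Table 9): RSV A, H1N1 and both B strains 1.3; RSV B 1.4; H3N2 1.7.
- n = 650 evaluable per group (Protocol 9.5).
- Correlation ρ between log Visit 1 titer and log 1-month titer: **not in the documents**. Assumed 0.1 to 0.7, the same for all six endpoints.

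**Step 1: reproduce the plan.** Noncentral-t power with df = 2n − 2 and noncentrality (0.405 − 0.105) / (SD × √(2/n)). For H3N2 the standard error is 1.7 × √(2/650) = 0.0943, the noncentrality is 0.300/0.0943 = 3.18, and power is 88.9%. SD 1.4 gives 97.1% and SD 1.3 gives 98.6%. The product of the six is 81.6%. All match Table 9, which confirms that the plan multiplies the six powers as if the tests were independent.

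**Step 2: adjust for baseline.** Residual SD = SD × √(1 − ρ²). At ρ = 0.5 the H3N2 SD is 1.7 × √0.75 = 1.472, the standard error is 0.0817, the noncentrality is 3.67, and power is 95.6%. The unadjusted analysis needs 650 per group; adjustment reaches the same precision with 650 × (1 − ρ²).

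| ρ (assumed) | H3N2 power | All-six power, ratio 0.9 | Adjusted n per group matching 650 unadjusted | All-six power, ratio 0.85 |
|---|---|---|---|---|
| none (plan) | 88.9% | 81.6% | 650 | 46% |
| 0.1 | 89.2% | 82.2% | 644 | 47% |
| 0.2 | 90.0% | 84.0% | 624 | 49% |
| 0.3 | 91.5% | 86.9% | 592 | 54% |
| 0.5 | 95.6% | 94.2% | 488 | 72% |
| 0.7 | 99.4% | 99.3% | 332 | 93% |

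The last column replaces 0.105 with −ln(0.85) = 0.163.

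**Step 3: set this against the sample cut.** With 7–8% nonevaluable, 2230 enrolled gives 1025 to 1036 per group and an unadjusted all-six power of about 97.5%. An adjusted analysis of 1400 has the precision of an unadjusted analysis of 2230 when 1 − ρ² = 1400/2230, that is ρ ≈ 0.61.

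**Step 4: what the H3N2 comparison must show.** The smallest observed GMR that passes is 0.667 × exp(1.962 × SE): 0.803 unadjusted, 0.796 at ρ = 0.3, 0.783 at ρ = 0.5 and 0.761 at ρ = 0.7.

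**The case against.** The strongest reply is that nothing is broken. A two-sample t-interval is valid under 1:1 randomization, it is the method the sample size was built on, and power still exceeds 80%. It also allows for chance baseline imbalance on average. That is right: the loss is of efficiency, not validity.

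Three points reduce the size of the gain.

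- **ρ is unknown.** The documents support prior exposure, but not how strongly baseline predicts the 1-month titer. At ρ = 0.1 the gain is under one point. For RSV, Visit 1 precedes the outcome by about one month in one group and two in the other, so even a common ρ across groups is uncertain.
- **The planning SDs are conservative.** Table 9 notes: "The maximum SD across all age/vaccine groups was used for each antigen/strain", and the reference study included adults aged 18 to 49. If every SD were 5% or 10% lower (assumed), unadjusted all-six power would be 87.3% or 91.8%.
- **The six tests are not independent.** With an assumed common correlation between endpoints of 0.3, 0.5 or 0.7, unadjusted all-six power is about 84%, 85% or 87%. The gain at ρ = 0.3 then falls from 5.3 points to 4.5, 3.9 or 3.3.

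The change also costs more than wording. It alters the primary analysis, and both documents say a major change of that kind must also appear in a protocol amendment.

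These caveats limit the benefit without showing a downside. One or two covariates cost one or two degrees of freedom out of about 1300, so little is lost if ρ is near zero. On the log scale the adjusted group effect targets the same GMR.

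**Conclusion.** The concern holds. All six primary GMRs ignore a baseline titer that the trial already collects and assays. The plan is valid as written but less precise than it could be, at a point where power is thin. At a true ratio of 0.9, all-six power would rise from 81.6% to 86.9%, 94.2% or 99.3% for ρ of 0.3, 0.5 or 0.7, and by about 0.6 to 2.4 points for ρ of 0.1 to 0.2. If the true ratio were 0.85, it would rise from 46% to about 54%, 72% or 93% for ρ of 0.3, 0.5 or 0.7.

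These figures rest on an assumed ρ common to all endpoints, the Table 9 SDs, 650 evaluable per group, and independent tests as in Table 9. That the facts are as stated and that adjustment is the better choice is firm. The exact gain is not. The change should be made, but the unadjusted analysis would not invalidate the trial.

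**What to change.** Amend Protocol 9.3.1.2.3 and SAP 5.2.2.3, 6.1.1.1 and 6.1.2.1 before unblinding:

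- **Model.** The primary GMR is the exponentiated group effect, with its 95% CI, from an ANCOVA of 1-month log titer on group, log Visit 1 titer for the same assay or strain, and age group (65–74, ≥75). The gains above count the baseline titer only; age group is added because SAP 6.4 already uses it.
- **Baseline.** Use Visit 1 in both groups, including for RSV in the sequential group. The fold-rise rule in SAP 3.1.4.1 takes Visit 2 there, which is after randomization and after influenza vaccination, and should not serve as the covariate.
- **Below LLOQ.** State that covariate values below LLOQ are set to 0.5 × LLOQ, the general rule in SAP 5.3.2, and not to the value that section uses for some fold-rise denominators.
- **Missing baseline.** The evaluable populations do not require a valid Visit 1 result. State a rule, for example imputing the overall mean for the covariate only, and word it as an explicit exception to the no-imputation rule in SAP 5.3.2. Outcomes stay unimputed.
- **Supportive analysis.** Keep the unadjusted GMR and t-interval.

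The cost is a protocol amendment with its approvals, an SAP revision and a few lines of code. No new visits, samples or assays are needed. If an amendment is not practical, prespecify the ANCOVA GMR as a supplementary analysis. That would show the added precision, but would leave the primary decision on the unadjusted interval.

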5.2.2.4. Reverse Cumulative Distribution Curves

Empirical RCDCs will plot proportions of participants with values equal to or exceeding a specified assay value versus the indicated assay value, for all observed assay values. Data points will be joined by a step function with the line first going down and then to the right to the next assay value.

5.3. Methods to Manage Missing Data

5.3.1. Safety Data

Standard algorithms for handling missing AE dates and missing AE severity will be applied as described in the safety rulebook summary.

Missing data handling rules on the safety data are described in detail in the corresponding endpoint sections.

5.3.1.1. Reactogenicity Data

For derived variables based on reactogenicity data, if any day of the 7-day e-diary is available, the "any day (Days 1-7)" data will be considered nonmissing.

The reactogenicity data are collected through the e-diary, which does not allow participants to skip the question. Therefore, for a specific day, if the e-diary data are transferred for that day, all of the reactogenicity data for the participant on that day are nonmissing. No missing reactogenicity data will be imputed other than what is described in [Section 3.1](#). In summary, for any participant with all 7 days of the e-diary missing, this will not be included in the analysis (ie, assuming MCAR). If only 1 to 6 days of e-diary data are transferred, the reactogenicity data for the missing day(s) are considered as answering "no" for all reactions. This is based on the common assumption that no reports means no events.

Based on data from available studies, the missing data for reactogenicity are minimal, which is consistent with Li et al.⁵ No sensitivity analysis is planned for reactogenicity data.

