3.1.3. Primary Safety Endpoints

In general, e-diary data that are confirmed as errors will not be used for derivation or analysis. Below is a list of safety endpoints that will be derived.

- Local reactions within 7 days after Vaccination 1 (Visit 1).
- Local reactions within 7 days after Vaccination 2 (Visit 2).
- Systemic events within 7 days after Vaccination 1 (Visit 1).
- Systemic events within 7 days after Vaccination 2 (Visit 2).
- AEs within 1 month after Vaccination 1 (Visit 1).
- AEs within 1 month after Vaccination 2 (Visit 2).
- SAEs within 1 month after Vaccination 1 (Visit 1).
- SAEs within 1 month after Vaccination 2 (Visit 2).

3.1.3.1. Local Reactions Within 7 Days After Vaccination 1

The local reactions reported in the e-diary are redness, swelling, and pain at the injection site from Day 1 through Day 7 after Vaccination 1, where Day 1 is the day of vaccination with RSVpreF or placebo at Visit 1. This section describes derivations with details for the assessment of local reactions: any presence, maximum severity, duration, and onset day of local reactions, in addition to presence of local reactions on each day.

3.1.3.1.1. Presence of Local Reactions Within 7 Days After Vaccination 1

For the summary of the presence (yes or no) of a local reaction during the interval from Day 1 through Day 7 after Vaccination 1, where Day 1 is the day of Vaccination 1, the following 2 variables are derived for each participant included in the reactogenicity subset:

1. Presence (yes or no) of each local reaction on any day (Day 1 through Day 7).

The derivation is described in Table 3.

Table 3. Derived Variables for Each Local Reaction

Variable ^a	Yes (1)	No (0)	Missing (.)
Any day (Days 1-7)	The participant reports the reaction as “yes” on any day (Days 1-7).	The participant reports the reaction as “no” on all 7 days or as a combination of “no” and missing on all 7 days.	The participant reports the reaction as missing on all 7 days.

- a. The variable will be defined for each of the 3 local reactions.

2. Presence (yes or no) of any local reaction on any day (Day 1 through Day 7).

For any local reaction on any day, a similar definition can be applied as given in Table 4.

Table 4. Derived Variables for Any Local Reaction

Variable	Yes (1)	No (0)	Missing (.)

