3.1.3.1.4. Onset Day of Each Local Reaction

The onset day of each local reaction will be derived. Onset day is defined as the first day of reporting any severity.

For the onset day of each local reaction, if the participants report changes in severity of the local reaction, only the first day of reporting that specific local reaction will be counted.

3.1.3.1.5. Presence of Each and Any Local Reactions on Each Day and Any Day

Presence (yes or no) of each and any local reaction on each of the 7 days (Day 1 through Day 7) follows the derivation as described in [Table 6](#).

Table 6. Derived Variables for Each and Any Local Reaction on Each Day and Any Day

Variable	Yes (1)	No (0)	Missing (.)
Each local reaction on a specific day	The participant reports the reaction on a specific day for a specific local reaction.	The participant reports the reaction as “no” on that specific day.	The participant reports the specific local reaction as missing on that specific day.
Any local reaction on a specific day	The participant reports the reaction on a specific day for any of the 3 local reactions.	The participant reports the reactions as “no” or a combination of “no” or missing on that specific day across all 3 local reactions.	The participant reports all 3 local reactions as missing on that specific day.
Each local reaction on any day	The participant reports that local reaction on any day (Days 1-7).	The participant reports the local reaction as “no” or a combination of “no” and missing across all 7 days.	The participant reports the local reaction as missing on all 7 days.
Any local reaction on any day	The participant reports any local reaction on any day (Days 1-7).	The participant reports the reactions as “no” or missing across all 7 days and across all 3 local reactions.	The participant reports all 3 local reactions as missing on all 7 days.

3.1.3.2. Local Reactions Within 7 Days After Vaccination 2

The variables to be derived for local reactions reported in the e-diary within 7 days after Vaccination 2 is similar to that after Vaccination 1.

Day 1 is the day of vaccination with RSVpreF or placebo at Visit 2.

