3.1.3.3. Systemic Events

Systemic events, including fever, fatigue, headache, vomiting, nausea, diarrhea, muscle pain, and joint pain, are reported via the e-diary from Day 1 through Day 7 after Vaccination 1, where Day 1 is the day of Vaccination 1 with RSVpreF or placebo, and from Day 1 through Day 7 after Vaccination 2, where Day 1 is the day of Vaccination 2 with RSVpreF or placebo. The derivations for the systemic events as described below will be handled similarly to the way local reactions are handled for the presence for each participant, severity level, duration, onset day, and systemic event on each and any day.

1. Presence (yes or no) of each systemic event on any day (Day 1 through Day 7) after Vaccination 1.
2. Presence (yes or no) of any systemic event on any day (Day 1 through Day 7) after Vaccination 1.
3. Maximum severity of each systemic event on any day (Day 1 through Day 7) after Vaccination 1.

4. Maximum severity of any systemic event on any day (Day 1 through Day 7) after Vaccination 1.
5. Duration of each systemic event after Vaccination 1.
6. Onset day of each systemic event after Vaccination 1.
7. Presence (yes or no) of each systemic event on each and any of the 7 days after Vaccination 1.
8. Presence (yes or no) of any systemic event on each and any of the 7 days after Vaccination 1.
9. Presence (yes or no) of each systemic event on any day (Day 1 through Day 7) after Vaccination 2.
10. Presence (yes or no) of any systemic event on any day (Day 1 through Day 7) after Vaccination 2.
11. Maximum severity of each systemic event on any day (Day 1 through Day 7) after Vaccination 2.
12. Maximum severity of any systemic event on any day (Day 1 through Day 7) after Vaccination 2.
13. Duration of each systemic event after Vaccination 2.
14. Onset day of each systemic event after Vaccination 2.
15. Presence (yes or no) of each systemic event on each and any of the 7 days after Vaccination 2.
16. Presence (yes or no) of any systemic event on each and any of the 7 days after Vaccination 2.

The grading scale for systemic events is provided in [Table 7](#).

Table 7. Grading Scale for Systemic Events

	Mild Grade 1	Moderate Grade 2	Severe Grade 3	Grade 4^a
Fatigue (= tiredness in diaries)	Does not interfere with activity	Some interference with activity	Prevents daily routine activity	Emergency room visit or hospitalization for severe fatigue

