6.1.3.2. Supplementary Analysis

To support the assessment of reactogenicity, the endpoints below, as specified in [Section 3.1.3.1](#), will be summarized per the supplemental analysis with the same analysis population:

- Duration (days) of each local reaction and each systemic event after each vaccination.
- Onset day of each local reaction and each systemic event after each vaccination.
- Presence of each and any local reaction and each and any systemic event, on each of the 7 days and for “any day (Days 1-7).”

The presentation of the results will include a basic descriptive summary without the 95% CIs ([Section 5.2.1](#)).

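### Minor conflict in the SAP: 5.3.1.1 counts untransmitted e-diary days as *no*, while the specific-day rows of Table 6 code them as missing, so the supplementary day-by-day reactogenicity rates have two possible denominators

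*SAP*

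**What the plan says.** SAP 5.3.1.1 deals with diaries in which some but not all of the 7 days arrive: "If only 1 to 6 days of e-diary data are transferred, the reactogenicity data for the missing day(s) are considered as answering". The answer it supplies is *no*, whatever the reaction. It adds that the e-diary does not let a participant skip a question, so a transmitted day is complete. Earlier in the same paragraph it sets a limit: "No missing reactogenicity data will be imputed other than what is described in" Section 3.1. Its parent section, SAP 5.3.1, points the same way: "Missing data handling rules on the safety data are described in detail in the corresponding endpoint sections".

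Table 6 (SAP 3.1.3.1.5, so within Section 3.1) defines presence on a specific day. For each local reaction, the missing code applies when: "The participant reports the specific local reaction as missing on that specific day". For any local reaction, it applies when all three are missing that day. Systemic events take the same derivations; they "will be handled similarly to the way local reactions are handled".

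The specific-day variables are reported in SAP 6.1.3.2, the supplementary analysis: "Presence of each and any local reaction and each and any systemic event, on each of the 7 days". That summary is descriptive and carries no confidence intervals.

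**The concern.** A diary day is either transmitted whole or not at all. Every untransmitted day in a partly completed diary therefore meets both the *no* rule of 5.3.1.1 and the missing code of Table 6. A programmer who follows 5.3.1.1 literally keeps that participant in the day's denominator as reaction-free. A programmer who follows Table 6 leaves the participant out. The two would produce different daily tables from the same data, and the literal rule always gives the lower rate whenever the rate is above zero.

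Missed days can happen: Protocol 8.2.3 allows entries only within a fixed window each day, and Protocol 8.9.1 sets it at 4:00 PM to midnight. What is at stake is the reproducibility of the planned day-by-day tables, for local reactions and systemic events after both vaccinations. It is not any test or main safety rate.

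**Working it through.** The documents give no daily reaction rate and no share of untransmitted days, so there is no plan figure to reproduce. The check has three parts.

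**1. Which derived variables change.** Take one reaction over 7 days, each day yes, no or missing. There are 3^7 = 2187 patterns. Removing the all-missing pattern (1) and the complete patterns (2^7 = 128) leaves 2058 partly completed diaries. Derive each variable with missing days left missing, then with missing days set to *no*:

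| Variable | SAP definition | Patterns that differ |
|---|---|---|
| Any-day presence | Table 3: *no* plus missing is already No | 0 of 2058 |
| Onset day | 3.1.3.1.4: first day reported | 0 of 2058 |
| Last recorded reaction day | 3.1.3.1.3, diary part | 0 of 2058 |
| At least one specific-day value | Table 6 | 2058 of 2058 |

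Maximum severity (SAP 3.1.3.1.2) cannot change either: adding grade 0 to a set with at least one observed grade leaves its maximum as it was. This holds for all 5^7 − 1 = 78,124 patterns of grade 0 to 3 or missing with at least one transmitted day. These counts list logical possibilities; they do not predict how often such diaries occur.

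**2. Duration.** SAP 3.1.3.1.3 uses the last day recorded in the diary or, if the reaction is unresolved in the diary period, the end date from the CRF. Protocol 8.2.3 requires sites to obtain that stop date for a reaction ongoing on the last completed diary day. Under this wording the imputation has no effect. A difference could arise only if an imputed *no* after the last transmitted day were taken as resolution, so that the CRF date was not used. The patterns open to this have a reaction on the last transmitted day *k* (*k* = 1 to 6) and nothing after it: 1 + 3 + 9 + 27 + 81 + 243 = 364 of the 2058.

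**3. Size of the shift in daily rates.** Let N be the participants with at least one transmitted day, m those missing the day in question, and y those reporting the reaction that day.

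- Table 6 rate: y / (N − m)
- Literal 5.3.1.1 rate: y / N = [y / (N − m)] × (1 − m/N)
- Difference: Table 6 rate × m/N

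For illustration take N = 700, the planned group size in Protocol 4.1. With m = 35 (5%) and y = 133, Table 6 gives 133/665 = 20.0% and the literal rule gives 133/700 = 19.0%. With assumed Table 6 rates of 5% to 40% and assumed missing shares of 1% to 10%, the literal rule gives:

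| Table 6 rate | 1% missing | 2% | 5% | 10% |
|---|---|---|---|---|
| 5% | 4.95% | 4.90% | 4.75% | 4.50% |
| 10% | 9.9% | 9.8% | 9.5% | 9.0% |
| 20% | 19.8% | 19.6% | 19.0% | 18.0% |
| 40% | 39.6% | 39.2% | 38.0% | 36.0% |

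**The case against.** The strongest reply is that the SAP already says which rule governs. Section 5.3.1 sends the reader to the endpoint sections. Section 5.3.1.1 opens with the any-day variable, bars imputation beyond Section 3.1, and only then gives the *no* rule as a summary. SAP 6.1.3.1 cites that rule for the main analysis, while 6.1.3.2 carries over the analysis population and does not mention it. SAP 3.3.3 already defines transmission for a given day. Under the literal reading, Table 6's specific-day missing code would also have little left to do: wholly missing diaries are excluded, which leaves entries removed because "e-diary data that are confirmed as errors will not be used for derivation or analysis". All of this stands, and it favours Table 6. What it does not do is limit the *no* sentence, which is written at day level and, read that way, goes beyond the limit set in its own paragraph.

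A second reply is that the effect is small. The SAP says: "Based on data from available studies, the missing data for reactogenicity are minimal". This also stands; the larger shifts above need missing shares that the SAP does not expect.

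Third, Table 6 could be changed to match 5.3.1.1, which gives a reason: no report is taken to mean no event. Either direction would remove the conflict. Table 6 is the better anchor because it lies in the section to which 5.3.1.1 defers, and because Protocol 9.1.1 rules out imputing other missing safety information (although the SAP may modify the protocol).

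**Conclusion.** The conflict is real but minor. Two stated rules give different denominators for one planned supplementary output, and the literal *no* rule lowers each daily rate by the rate times the share missing that day. At a 20% rate the shift is 0.2 points with 1% missing and 1.0 point with 5% missing. The rates and missing shares are assumptions; the direction and the formula are not.

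A reader might infer that the main reactogenicity rates are understated because of this conflict. The documents do not support that: any-day presence and maximum severity already treat *no* plus missing as No or grade 0, so both rules give the same result. A reader might also infer that duration is beyond reach whatever the programmer does. That is too strong. It is unchanged as worded, but only if an imputed *no* is not taken as resolution and the CRF end date is used where it applies. Duration is itself supplementary and descriptive, so this does not raise the severity. No immunogenicity result, power figure or error rate is involved.

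**What to change.** In SAP 5.3.1.1:

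- Limit the *no* convention to the any-day (Days 1-7) and maximum-severity variables.
- State that specific-day rates, for local reactions and systemic events, follow Table 6: an untransmitted day is missing and is left out of that day's denominator, and the daily N is shown.
- State that an imputed *no* does not count as resolution when duration is derived; SAP 3.1.3.1.3 continues to apply.

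The cost is a few sentences. The protocol, CRF, data collection and number of tables stay the same. The one drawback is that denominators vary from day to day, which is why each daily rate needs its N beside it.
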